Study treatments will continue until progressive disease (PD) is BICR-verified or further confirmed by the investigator, unacceptable adverse events (AEs) or intercurrent illness prevents further administration of treatment, death or withdrawal of consent. When a subject is first identified with PD by the investigator, the site will request PD to be verified by BICR. Subjects who are clinically stable may continue treatment while waiting for BICR verification. Progressive disease status may be further confirmed by subsequent scans at the site. Detailed descriptions of imaging-based disease assessments, PD verification by BICR, and PD confirmation at the site are provided in Section 7.1.2.7.2 and Section 7.1.2.7.6.

For the combination arm, pembrolizumab will be administered for a maximum of 35 doses. If a subject remains progression-free after 35 doses of pembrolizumab, treatment with axitinib will be continued as monotherapy until PD is verified by BICR or further confirmed by the investigator. In addition, if 1 of the 2 compounds needs to be discontinued because of toxicity or intolerance, treatment with the other compound as monotherapy will be continued until PD is verified by BICR or further confirmed by the investigator. For both arms, in the event that a complete response (CR) has been observed in a subject, study treatment may be discontinued at the discretion of the investigator after the CR has been confirmed and after a minimum of 8 cycles of treatment (~24 weeks) in the pembrolizumab plus axitinib arm or 4 cycles of treatment (~24 weeks) in the sunitinib arm have been received. Detailed criteria for study treatment discontinuation and re-treatment are described in Section 5.8.

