
Scenario 4: ALT/AST > 10 × ULN without clinically significant signs of hepatic dysfunction
 
Consultation with Sponsor medical monitor is required prior to rechallenge
	
 • If initial event is likely to be immune-mediated by pembrolizumab: 
 ○ discontinue pembrolizumab and rechallenge with axitinib as monotherapy • If initial event is likely related to axitinib and unlikely due to pembrolizumab: 
 ○ Rechallenge with pembrolizumab monotherapy • If event is potentially related to a contribution of both drugs (such as upfront steroid use with improvement along with axitinib interruption), subject may be rechallenged with axitinib at reduced dose: 
 ○ If no recurrence, continue with axitinib monotherapy ○ If ALT/AST elevation recurs, discontinue axitinib and may be rechallenged with pembrolizumab • Permanently discontinue pembrolizumab if ALT/AST recurrence is >5× ULN or interrupt pembrolizumab if ALT/AST recurrence is >3 to 5× ULN after its rechallenge and manage per Section 5.2.2.1. • Permanently discontinue axitinib if ALT/AST recurrence is >5× ULN or interrupt axitinib if ALT/AST recurrence is >3 to 5× ULN and rechallenge with reduced dose.

Note: 1. Subject should have weekly monitoring with liver tests (i.e., liver enzyme and function tests) for 2-3 weeks after each drug rechallenge. 2. If both study drugs are discontinued due to a hepatic event, subjects should be monitored until AE resolution as per protocol and continue imaging and survival follow-up as per protocol. 3. Events under Scenario 1, 3, and 4 must be reported to the Sponsor as Events of Clinical Interest (see Section 7.2.3.2 for details). 4. Liver tests include liver enzyme (ALT, AST, and ALP) and liver function (bilirubin and PT/INR) tests.
 
Abbreviations: ALP = alkaline phosphatase; ALT = alanine aminotransferase; AST = aspartate aminotransferase; INR = international normalized ratio; PT = prothrombin time.
	

5.2.2.4 Dose Modification Guidelines for Adverse Events Potentially Associated with Sunitinib Treatment

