6.0 TRIAL FLOW CHART

6.1 Trial Flow Chart (Pembrolizumab in Combination With Axitinib)

Trial Period:	Screening	Treatment Cycles (1 cycle = 21 days) ^a												End of Treatment	Post-Treatment				
Scheduled Clinic Visit: Clinic Visit Windows (Days):	Screening	Cycles 1-8								To be repeated Beyond Cycle 12				End of Treatment	Safety Follow-up 30 days from last dose ± 3	Imaging Follow-up Q6W or Q12W ^b (± 7)	Survival Follow-up Q12W ^c (± 7)		
		C1	C2	C3	C4	C5	C6	C7	C8	C9	C10	C11	C12						
	D1 ^a	D8	D1	D1	D1	D1	D1	D1	D1	D1	D1	D1	D1					± 3	± 3
ADMINISTRATIVE PROCEDURES																			
Informed Consent ^d	X																		
Informed Consent - FBR	X																		
Inclusion/Exclusion Criteria	X																		
Subject Identification Card ^e	X													X					
Demographics & Medical History	X																		
Prior and Concomitant Treatment/Medication Review ^f	X	X	X	X	X	X	X	X	X	X	X	X	X	X	X	X	X		
Post-study Anti-cancer Therapies																X	X	X	
Survival Status ^g		←----->															X		
STUDY DRUG ADMINISTRATION/COMPLIANCE																			
Pembrolizumab Infusion ^h		X		X	X	X	X	X	X	X	X	X	X	X	X				
Axitinib Dosing ^h		X (continuous BID dosing)																	
Dispense Axitinib and Dosing Diary ⁱ		X		X	X	X	X	X	X	X	X	X	X	X	X				
Review Axitinib Compliance ⁱ				X	X	X	X	X	X	X	X	X	X	X	X	X			
CLINICAL PROCEDURES/ ASSESSMENTS																			
AE Monitoring	X	X	X	X	X	X	X	X	X	X	X	X	X	X	X	X	X ^j	X ^j	
Full Physical Examination	X														X				
Directed Physical Examination				X	X	X	X	X	X	X	X	X	X	X					
Vital Signs ^k	X		X	X	X	X	X	X	X	X	X	X	X	X	X	X			

Trial Period:	Screening	Treatment Cycles (1 cycle = 21 days) ^a												End of Treatment	Post-Treatment		
		Cycles 1-8								To be repeated Beyond Cycle 12					Safety Follow-up 30 days from last dose	Imaging Follow-up Q6W or Q12W ^b	Survival Follow-up Q12W ^c
Scheduled Clinic Visit:	Screening	C1	C2	C3	C4	C5	C6	C7	C8	C9	C10	C11	C12	End of Treatment			
Clinic Visit Windows (Days):	-28 to -1	D1 ^a	D8	D1	D1	D1	D1	D1	D1	D1	D1	D1	D1		± 3	(± 7)	(± 7)
12-Lead ECG ^l	X					X				X					X		
Karnofsky Performance Status ^m	X			X	X	X	X	X	X	X	X	X	X	X	X		
EFFICACY MEASUREMENTS – TUMOR IMAGING																	
Chest, Abdomen, Pelvis (CAP)	X ⁿ									X ^o							X ^p
Bone Scan	X ^{n,q}									X ^q							X ^q
Brain Scan	X ^{n,r}									X ^r							X ^r
PATIENT-REPORTED OUTCOMES																	
QoL (FKSI-DRS, EORTC QLQ-C30, EQ-5D-3L) ^s		X		X	X	X	X	X	X	X	X	X	X	X	X	X	

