
diagnostic quality and within the 28 day window. See Sections 7.1.2.7.1 and 7.1.2.7.2 for additional imaging requirement at baseline and follow up if RCC metastatic lesions identified outside of the standard imaging assessment anatomic regions per protocol.
 
o. Imaging after randomization will be performed at Week 12 (84 days ±7 days), then Q6W (42 days ±7 days) through Week 54, then Q12W (84 days ±7 days) thereafter until PD is BICR verified. Imaging visit window may be ± 14 days after Week 104. Unscheduled imaging can be performed as clinically indicated. The timing of imaging assessments should follow calendar days from randomization and should not be adjusted for dose delays or cycle starts. Imaging anatomic coverage should be the same as that at screening; see Section 7.1.2.7.2 for details.
 
p. Subjects who discontinue treatment for reasons other than BICR verified PD should continue with imaging assessments per the protocol defined schedule as outlined in footnote “n” until: 1) PD is BICR verified, 2) initiation of a new anti-cancer treatment, 3) death, 4) withdrawal of consent or 5) study conclusion or early termination, whichever occurs first.
 
q. Baseline bone scan is required for all subjects. If a subject has a positive baseline bone scan, after randomization, bone scans will be performed at Week 18 (Day 126 ± 7 days) and should continue to be performed Q12W (84 days ±7 days) through Week 54, subsequently Q24W (168 days ±7 days) until PD is BICR verified or further confirmed by the investigator. The timing of imaging assessments should follow calendar days from randomization and should not be adjusted for dose delays or cycle starts. Bone scans must be performed for the confirmation of Complete Response (CR) for subjects with a positive bone scan at baseline.
 
r. A brain scan will be performed during screening for subjects with brain metastasis to ensure subject is stable. After randomization, brain imaging should be performed as clinically indicated and to confirm a CR in subjects with brain metastasis at baseline.
 
s. At each clinic visit, Quality of Life (QoL) measurements should be performed before all other study procedures and assessments, including the dosing of study medication. QoL will be assessed on D1 visit of every cycle from C1-C8, D1 visit of every other cycle from C9 to C19, D1 visit of every 4 cycles from C19 (approximately Week 54) until study treatment is discontinued. In addition, QoL is to be assessed at the Treatment Discontinuation visit and 30-day Safety follow-up visit. QoL is only assessed once if these two visits are combined.
 
t. Pregnancy tests – Urine or serum β-hCG: See Section 5.1.2 for pregnancy tests requirements for screening. If the randomization pregnancy test is more than 72 hours prior to the first dose of study treatment, it should be repeated. If urine pregnancy results are positive or cannot be confirmed as negative, a serum pregnancy test performed by the local study site laboratory will be required. Pregnancy tests (serum and/or urine tests) should be repeated if required by local guidelines. Monthly pregnancy testing should be conducted as per local regulations where applicable.
 
u. PT/INR, hematology, chemistry, urinalysis, and thyroid function testing will be performed at Screening (within 10 days of randomization), on Day 1 visit of every cycle (starting from C2), End of Treatment visit and at the Safety Follow-up visit. Routine safety laboratory values of chemistry and hematology results should be available prior to each pembrolizumab dosing.
 
v. Pre-dose trough PK and ADA samples for the pembrolizumab plus axitinib arm will be collected on Day 1 of Cycles 1, 3, 5, every 4 cycles thereafter (C9D1, C13D1, C17D1, ...) and 30 days after discontinuation. Pre-dose trough samples should be drawn within 24 hours prior to pembrolizumab infusion.
 
w. Additional post-dose peak PK samples will be drawn within 30 minutes after end of pembrolizumab infusion at Cycles 1 and 9. See Section 7.1.3.3 for additional guidance for PK sampling when dosing is interrupted/delayed.
 
x. Tumor tissue from an archival tissue sample or newly obtained biopsy should be submitted at Screening for biomarker analysis.
																	

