LABORATORY PROCEDURES/ ASSESSMENTS – Local Lab																		
Pregnancy Test ^t	X																	
PT/INRu ^t	X			X	X	X	X	X	X			X	X	X	X			
Hematology ^u	X			X	X	X	X	X	X			X	X	X	X			
Chemistry ^u	X			X	X	X	X	X	X			X	X	X	X			
Urinalysis ^u	X			X	X	X	X	X	X			X	X	X	X			
Thyroid Function Testing ^u	X			X	X	X	X	X	X			X	X	X	X			

Trial Period:	Screening	Treatment Cycles (1 cycle = 42 days) ^a											End of Treatment	Post-Treatment						
Treatment Cycle:	Screening	Cycles 1-4										To be repeated Beyond Cycle 6		Discon	Safety Follow-up	Imaging Follow-up	Survival Follow-up			
		C1			C2			C3		C4		C5	C6							
Scheduled clinic visit:		D1 ^a	D15	D29	D1	D29	D1	D29	D1	D29	D1	D1								
Clinic visit Windows (Days):	-28 to -1		± 3	± 3	± 3	± 3	± 3	± 3	± 3	± 3	± 3	± 3	± 3	± 3	± 3	± 3	End of Treatment	30 days from last dose (± 3 days)	Q6W or Q12W ^b (± 7 days)	Q12W ^c (± 7 days)
TUMOR BIOPSY/ ARCHIVAL TISSUE COLLECTION/ BLOOD FOR CORRELATIVE STUDIES																				
Tumor Tissue Collection	X ^v																			
Blood for genetic analyses ^w		X																		
Blood for ctDNA analyses ^x		X		X			X								X					
Blood for TCR repertoire ^x		X		X			X								X					
Blood for RNA analyses ^x		X		X			X								X					
Blood for plasma biomarker analyses ^x		X		X											X					
Blood for serum biomarker analyses ^x		X		X											X					

a. Each treatment cycle in the sunitinib arm is 6 weeks long (42 days ± 3 days). C1D1 denotes the first dose of study treatment, which can be on the date of randomization or within 3 days of randomization. See Section 5.2.3.4 for scenarios regarding dose interruptions.

b. Imaging Follow-up visits are for subjects who have discontinued study treatment without reaching BICR verified or further investigator confirmed PD. See footnotes “n” and “o” for further details.

c. Survival Follow-up may be conducted as a telephone call or a clinic visit Q12W (visit window is ± 7 days through Week 104 and ± 14 days after Week 104). Survival contact may be requested more frequently at the time of interim and final analysis or an eDMC safety review (see Section 7.1.5.3.4).

d. Written consent must be obtained prior to performing any protocol-specified procedures.

e. The Subject Identification Card should be dispensed at Screening and collected at the End of Treatment visit.

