
i. Subjects will be given a dosing diary for sunitinib when sunitinib bottles are provided; the diary should be returned at the next visit and assessed for dosing compliance. See details in Section 7.1.1.9.
 
j. After the end of treatment, each subject will be followed for 30 days for AE monitoring (SAEs will be collected for 90 days after the end of treatment or 30 days after the end of treatment if the subject initiates new anti-cancer therapy, whichever is earlier). See Section 7.2.3.1 for details.
 
k. Vital Signs will be assessed at Screening (within 10 days of randomization), Day 15 and Day 29 of C1 and Day 1 and Day 29 C2 to C4, then Day 1 of all subsequent visits, the End of Treatment visit and the Safety Follow-up visit. C1D15 will only collect BP and pulse rate. Height will only be collected at Screening and will be recorded in the vital signs form. See Section 7.1.2.4 for BP assessments at baseline and during treatment.
 
l. An ECG is performed at Screening (within 10 days of randomization), after the completion of every 2 cycles (12 weeks) on treatment (C3D1, C5D1, C7D1, C9D1,...) and Safety Follow-up.
 
m. KPS is assessed at Screening (within 10 days of randomization), on Day 29 of C1, Day 1 and D29 of cycle C2-C3, Day 1 of every cycle thereafter (C4D1, C5D1, C6D1,...) and Safety Follow-up.
 
n. Baseline imaging must be performed within 28 days prior to randomization. Scans performed as part of routine clinical management are acceptable for use as the screening scan if they are of diagnostic quality and performed within the 28 day window. See Section 7.1.2.7.1 for additional imaging requirements at baseline and follow-up in subjects with RCC metastatic lesions identified outside of the standard imaging assessment anatomic regions per protocol.
 
o. Imaging after randomization will be performed at Week 12 (84 days ± 7 days), then Q6W (42 days ± 7 days) through Week 54, then Q12W (84 days ± 7 days) thereafter until PD is BICR verified or further confirmed by the investigator. Imaging visit window can be ± 14 days after Week 104. Unscheduled imaging can be performed as clinically indicated. The timing of imaging assessments should follow calendar days from randomization and should not be adjusted for dose delays or cycle starts. Imaging anatomic coverage should be the same as that at screening; see Section 7.1.2.7.2 for details.
 
p. Subjects who discontinue treatment for reasons other than BICR verified PD should continue with imaging assessments per the protocol defined schedule as outlined in footnote n until: 1) PD is BICR verified or further confirmed by investigator, 2) initiation of a new anti-cancer treatment, 3) death, 4) withdrawal of consent or 5) study conclusion or early termination, whichever occurs first. See footnote B for Imaging Follow-up schedule and windows.
 
q. Baseline bone scan is required for all subjects. If a subject has a positive baseline bone scan, after randomization, bone scans will be performed at Week 18 (126 days ± 7 days) and should continue to be performed Q12W (84 days ± 7 days) through Week 54. After Week 54, subsequently Q24W (168 days ± 7 days) through Week 54 until PD is BICR verified or further confirmed by investigator. The timing of imaging assessments should follow calendar days from randomization and should not be adjusted for dose delays or cycle starts. Bone scans must be performed for the confirmation of Complete Response (CR) for subjects with a positive bone scan at baseline.
 
r. A brain scan will be performed during screening for subjects with brain metastasis to ensure subject is stable. During the trial, brain imaging should be performed as clinically indicated and to confirm a CR in subjects with brain metastasis at baseline.
																		

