
s. At each clinic visit, Quality of Life (QoL) measurements should be performed before all other study procedures and assessments, including the dosing of study medication. QoL will be assessed D1 and D29 visits of C1-C4; D1 visit of C5 to C10, and D1 visit of every other cycle from C10 (D1C10, D1C12) (approximately Week 54) until study treatment is discontinued. In addition, QoL is to be assessed at the Treatment Discontinuation visit and 30-day Safety Follow-up visit. QoL is only assessed once if these two visits are combined.
 
t. Pregnancy tests – Urine or Serum β-hCG: See Section 5.1.2 for pregnancy tests requirements for screening. If the randomization pregnancy test is more than 72 hours prior to the first dose of trial treatment, it should be repeated. If urine pregnancy results are positive or cannot be confirmed as negative, a serum pregnancy test performed by the local study site laboratory will be required. Pregnancy tests (serum and/or urine tests) should be repeated if required by local guidelines. Monthly pregnancy testing should be conducted as per local regulations where applicable.
 
u. PT/INR, hematology, chemistry, urinalysis and thyroid function testing will be performed at Screening (within 10 days of randomization), C1D29, C2D1, C2D29, C3D1, C3D29, Day 1 of every cycle thereafter (C4D1, C5D1, C6D1,...), the End of Treatment visit and the Safety Follow-up visit.
 
v. Tumor tissue from an archival tissue sample or newly obtained biopsy should be submitted at screening for biomarker analysis.
 
w. Samples should be collected for planned analysis of the association between genetic variants in germline/tumor DNA and drug response. If a documented law or regulation prohibits (or if the IRB/IEC does not approve) sample collection for these purposes, then such samples should not be collected at the corresponding sites. Leftover DNA extracted from planned genetic samples will be stored for Future Biomedical Research only if the subject signs the FBR consent. If the planned genetic analysis is not approved, but FBR is approved and consent is given, this sample will be collected for the purpose of FBR.
 
x. Blood for ctDNA, TCR repertoire, RNA analyses and blood for serum/plasma biomarker analyses should be collected pre-dose according to time points on the flow chart. Leftover samples may be kept for Future Biomedical Research if the subject signs the FBR consent.
																		

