8.6.2 Statistical Methods for Safety Analyses

Safety and tolerability will be assessed by clinical review of all relevant parameters including AEs, laboratory tests, and vital signs.

Tiered Approach

The analysis of safety results will follow a tiered approach (Table 19). The tiers differ with respect to the analyses that will be performed. For this protocol, there are no Tier 1 events.

Tier 2 parameters will be assessed via point estimates with 95% CIs provided for between-group comparisons; only point estimates by treatment group are provided for Tier 3 safety parameters.

Adverse events (specific terms as well as system organ class terms) will be classified as belonging to "Tier 2" or "Tier 3", based on the number of events observed. Membership in Tier 2 requires that at least 10% of the subjects in any treatment group exhibit the event; all other AEs and predefined limits of change will belong to Tier 3.

The threshold of at least 10% of subjects with events was chosen for Tier 2 event because the incidence rate would allow meaningful statistical assessments; events reported in less frequent than 10% of subjects would obscure the assessment of overall safety profile and add little to the meaningful interpretation. Because many 95% CIs may be provided without adjustment for multiplicity, the confidence intervals should be regarded as a helpful descriptive measure to be used in review, not a formal method for assessing the statistical significance of the between-group differences in AEs and predefined limits of change.

Continuous measures such as changes from baseline in laboratory values and vital signs that are not pre-specified as Tier 1 safety parameters will be considered Tier 3 safety parameters. Summary statistics for baseline, on-treatment, and change from baseline values will be provided by treatment group in table format.

In addition, the broad clinical and laboratory AE categories consisting of the percentage of subjects with Grade 3-5 AE (incidence $\geq 5\%$ of subjects in one of the treatment groups) and any SAE (incidence $\geq 5\%$ of subjects in one of the treatment groups) will be considered Tier 2 endpoints.

The threshold of at least 5% of subjects with events was chosen for Tier 2 Grade 3-5 AEs and SAEs because the incidence rate would allow meaningful statistical assessments; those AEs are expected to happen less frequent than specific AEs/SOCs but important for overall safety profile assessment.

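### After Week 24 sunitinib subjects are scheduled for testing half as often as combination subjects, so Section 8.6.2 can show a combination-arm excess of short, test-detected AEs when true rates are equal

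*Combined protocol and SAP*

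**What the plan says.** **Cycle lengths.** Section 6.1 sets 21-day cycles for the combination arm. For sunitinib, Section 6.2 footnote a says: "Each treatment cycle in the sunitinib arm is 6 weeks long (42 days ± 3 days"). Section 2.1 puts the two on one time scale, with "8 cycles of treatment (~24 weeks) in the pembrolizumab plus axitinib arm or 4 cycles of treatment (~24 weeks) in the sunitinib arm".

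**Combination visits and tests (Section 6.1, footnotes k and u).** There is one extra visit at C1D8. After that, vital signs are taken on Day 1 of every cycle, and the safety laboratory panel is drawn "on Day 1 visit of every cycle (starting from C2), End of Treatment visit and at the Safety Follow-up visit". Section 5.2.3.4 keeps this 21-day schedule going until both drugs have stopped.

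**Sunitinib visits and tests (Section 6.2).** Footnote k puts vital signs on "Day 15 and Day 29 of C1 and Day 1 and Day 29 C2 to C4, then Day 1 of all subsequent visits". Footnote u puts the laboratory panel at "C1D29, C2D1, C2D29, C3D1, C3D29, Day 1 of every cycle thereafter (C4D1, C5D1, C6D1" and so on. C4D29 is therefore a visit without a laboratory draw.

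**Safety analysis (Section 8.6.2).** "Membership in Tier 2 requires that at least 10% of the subjects in any treatment group exhibit the event"; the cut-off is 5% for SAEs and Grade 3-5 AEs. Tier 2 terms get a Miettinen and Nurminen 95% CI for the difference in the percentage of subjects affected. The section states no time window and no adjustment for exposure or for frequency of assessment. Section 8.12 summarizes exposure in cycles, whose lengths differ between arms.

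**The concern.** Section 7.2 counts an abnormal laboratory finding as a possible AE and has AEs recorded at each examination. An abnormality that causes no symptoms and resolves by itself is normally found only if a test falls while it is present. If one arm is tested every 3 weeks and the other every 6, equal true rates give unequal observed percentages. This is separate from differing time on treatment, because it arises even when exposure is equal.

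The terms at risk are prominent for this regimen. In the Phase 1b data (Table 2) increased ALT was reported in 34.6% of subjects, increased AST in 30.8% and proteinuria in 21.2%. Hypertension (36.5%) is exposed to a lesser extent, because blood pressure is also measured at home. At stake is how the Tier 2 intervals for such terms are read: part of an apparent excess over sunitinib could come from the visit schedule.

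**Working it through.** **1. Time scale.** 8 × 21 = 168 days and 4 × 42 = 168 days, so both arms reach Week 24 together, as Section 2.1 says. As a second check, the quality-of-life footnotes place C19 and C10 at about Week 54: 18 × 3 = 54 and 9 × 6 = 54.

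**2. Scheduled contacts after C1D1, read from the flow charts.**

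- Combination visits: Week 1, then Weeks 3, 6, 9, … Draws: Weeks 3, 6, 9, …
- Sunitinib visits: Weeks 2, 4, 6, 10, 12, 16, 18, 22, 24, then every 6 weeks. Draws: Weeks 4, 6, 10, 12, 16, 18, 24, then every 6 weeks.

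| Period | Visits, combination vs sunitinib | Draws, combination vs sunitinib |
|---|---|---|
| To Week 18 inclusive | 7 vs 7 | 6 vs 6 |
| To Week 24 inclusive | 9 vs 9 | 8 vs 7 |
| After Week 24, to Week 54 | 10 vs 5 | 10 vs 5 |

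Draws diverge from Week 18 and visits from Week 24.

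**3. How much treatment time is affected.** Inputs are from Section 8.9: control median PFS 13 months, HR 0.60 (so 13/0.60 = 21.7 months for the combination), exponential times and 15-month accrual. I assume uniform accrual and treatment until progression. With hazard λ = ln 2/median, w = 24 weeks (5.5 months) and follow-up f spread uniformly over T−15 to T months, the share of on-treatment time after Week 24 is the average of (e^(−λw) − e^(−λf))/λ divided by the average of (1 − e^(−λf))/λ. At T = 22 months this is 52% (sunitinib) and 56% (combination). At T = 43 months it is 70% and 76%.

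**4. Detected incidence when true rates are equal.** The documents give no episode rates or durations, so these are assumptions: 0.2 episodes per patient-year in both arms, counting episodes that would be reported as an AE if a test found them; fixed duration d; everyone treated for 54 weeks; scheduled draws only. An episode is found if a draw falls within d weeks of onset. Let W be the weeks of onset time so covered. Then

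detected incidence = 1 − exp(−0.2 × W/52.18).

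There are 18 combination draws and 12 sunitinib draws to Week 54. For d = 2 the covered windows do not overlap:

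- Combination: W = 18 × 2 = 36; 1 − exp(−0.138) = 12.9%.
- Sunitinib: W = 12 × 2 = 24; 1 − exp(−0.092) = 8.8%.

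| Episode length | W, combination vs sunitinib | Detected, combination vs sunitinib |
|---|---|---|
| 1 week | 18 vs 12 | 6.7% vs 4.5% |
| 2 weeks | 36 vs 24 | 12.9% vs 8.8% |
| 3 weeks | 54 vs 33 | 18.7% vs 11.9% |
| 4 weeks | 54 vs 42 | 18.7% vs 14.9% |
| 6 weeks | 54 vs 54 | 18.7% vs 18.7% |

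At 0.4 per patient-year, 2-week episodes give 24.1% vs 16.8%. Counting only the draws after Week 24 up to Week 54, at 0.2 and 2 weeks, W is 20 vs 10 and the result 7.4% vs 3.8%.

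**5. Effect on the interval.** A separate model assumed a true 52-week incidence of 20% in both arms, all subjects treated to Week 52, scheduled draws only and 430 subjects per arm (861/2, rounded). Detected incidence was 13.1% vs 8.6% for 14-day abnormalities and 19.7% vs 18.7% for 42-day ones. The chance that a nominal 95% comparison excludes zero was about 55% and 6%.

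**6. Restriction to equal draws.** To Week 18, at 0.2 per patient-year, 2-week episodes give W = 12 in both arms and 4.5% vs 4.5%. Three-week episodes give W = 18 vs 15 and 6.7% vs 5.6%. The gap is removed or narrowed.

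**The case against.** Much of the opposing case stands, and it limits the reach of the point.

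- **Not all toxicity.** A reader might infer that any equal toxicity will look worse on the combination. The documents do not support that. AEs are reportable through 30 days after the last dose and SAEs within 24 hours, whatever the visit schedule. Unscheduled procedures are allowed (Section 7.1). Section 5.6.1 encourages home blood-pressure readings in both arms and asks subjects to contact the site when readings are high. Symptomatic AEs and SAEs are largely unaffected, and hypertension only partly affected.
- **Not the laboratory tables' intervals.** A reader might infer biased between-arm CIs for laboratory changes or predefined limits of change. Table 19 places these in Tier 3, with no between-arm CI. The bias reaches an interval only through findings reported as AE terms.
- **Not Tier 2 entry.** In the example one arm is above 10% and the other below. One arm is enough for entry, so the term gets its interval either way.
- **Not the extra liver tests.** Table 10 says "Subject should have weekly monitoring with liver tests (i.e., liver enzyme and function tests) for 2-3 weeks after each drug rechallenge", and Section 5.2.2.3.1 adds twice-weekly and weekly tests. These follow an ALT/AST rise already detected. They can raise the recorded maximum grade but do not create a first event. For sunitinib, Table 11 holds the dose until recovery, which implies repeat tests although no schedule is set.
- **Descriptive and conservative.** Section 8.6.2 calls the intervals descriptive, there are no Tier 1 events, and the bias runs against the experimental arm.

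The example is also near the upper end, because it assumes no unscheduled detection and full treatment to Week 54. What remains is that Section 8.6.2 still offers these intervals for between-arm assessment, and nothing in it tells the reader that testing was unequal.

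**Conclusion.** The point holds for a limited class of events: AE terms found mainly by testing, without symptoms, and lasting less than about 6 weeks. For these, equal true rates can appear as a combination-arm excess of about 4 percentage points (12.9% vs 8.8%) at 0.2 two-week episodes per patient-year. In the same model the gap is about 2 points for 1-week episodes, about 7 for 3-week episodes and nil at 6 weeks. The visit and draw counts come from the flow charts. The episode rates, durations, equal 54-week treatment and detection at scheduled draws only are assumptions. That the comparison covers the whole treatment period is inferred, since Section 8.6.2 states no window. No efficacy result or alpha-controlled test is affected. The matter is worth correcting because the correction is cheap, but it does not undermine the safety analysis as a whole.

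**What to change.** Add to Section 8.6.2, or to the sSAP:

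1. A supplementary Tier 2 comparison restricted to AEs with onset by Week 24 (9 scheduled visits per arm), using onset by Week 18 (6 scheduled draws per arm) for laboratory-detected terms. List those terms in advance.
2. A footnote on the all-data AE and laboratory tables that scheduled testing is 2:1 thereafter (laboratory draws from Week 18, visits from Week 24).

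Keep the all-data tables as the main display. Late tables limited to the six-weekly visits common to both arms may look attractive but are not recommended. Those visits fall at the end of sunitinib's two-week break, and such tables would exclude unscheduled tests.

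The cost is some wording and a few tables from data already collected; no trial procedure changes. The restricted comparison omits late-onset events, and it equalizes the number of tests but not their spacing, so it is supportive only.
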